## 9.2. Adverse Events and reporting requirements/procedures

AEs are commonly encountered in participants receiving either desogestrel or the COCP. As the safety profiles of the both the IMPs used in this trial are well characterised, only selected ARs experienced during treatment will be elicited from participants.

The following are regarded as expected for the purpose of this trial and will be collected on the 30-, 60- and 90-day follow-up questionnaires, completed by the participant:

- Headaches
- Nausea
- Breast tenderness
- Mood changes
- Increased blood pressure
- Hair thinning or loss
- Fluid retention in ankles/feet
- Bloating
- Weight change
- Acne

Only the presence (and severity) or absence of the above will be routinely collected for this trial.

The MedDRA medical coding dictionary will be used for the coding of serious adverse events is documented in this protocol.

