## 8. Trial procedures and assessments

### 8.1. Summary of assessments

**Table 7-Trial Assessments**

Activity	Timepoint				
	Baseline	Randomisation	Follow-up (days)		
			30	60	90
Informed consent	X				
Baseline demographic data	X				
Perception of bleeding pattern			X	X	X
Bleeding status	X (recall over previous 90 days)			Once daily	
Randomisation		X			
Intervention: Desogestrel or COCP				Once daily	
Health Related Quality of life (EQ-5D-5L)	X		X	X	X
Capacity-wellbeing (ICECAP-A)	X		X	X	X
Acceptability			X	X	X
Global impression of treatment					X
Adverse effects of treatment			X	X	X
Adherence to treatment				Once daily	
Adherence to treatment return of blister packs					At the end of individual participation in the trial
Healthcare resource use	X		X	X	X
Gratitude voucher			X	X	X

Intention to continue treatment					X
---------------------------------	--	--	--	--	---

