#### 8.2.7. Follow-up procedures

In accordance with standard clinical practice, participants will not be required to revisit their sexual health service or GP as part of their participation in this trial. Following randomisation, the majority of follow-up information will be obtained directly from the participants (via questionnaires) and coordinated by the NCTU without further involvement from the recruiting site. Following the participant's completion of the trial, the site staff will be asked to reveal the treatment allocation to the participant (either as part of their 3-month standard care visit or via telephone call), confirm the participant's adherence to treatment (where possible) and confirm whether the participant intends to continue on their allocated treatment to manage their problem bleeding. Follow-up timepoints for the trial are detailed in Figure 2-Routine clinical assessment outcome flowchart.

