##### 14.2.2. Secondary outcomes

**Table 10-Secondary outcomes**

Outcome Measure	Definition or derivation
Participant's self-reported significant improvement in the bleeding pattern.	At day 30, 60 and 90 as for primary outcome

Participant's self-reported non-worsening of the bleeding pattern	The 5-point Likert scale will be dichotomised into a response of "improved significantly" or "improved slightly" or "no change" versus "worsened slightly" or "worsened significantly"
Participant self-reported bleeding pattern.	Total number of days, within the 90-day window, of: 
 
- no bleeding
 
- spotting
 
- bleeding
 

Longest duration of consecutive non-bleeding (no bleeding or spotting) whole days for each 30-day period within the 90 days.	Longest consecutive number of days with responses of no bleeding or spotting, in 90 days
Time to longest episode of consecutive non-bleeding whole days	Time to the first day of the longest consecutive number of days with responses of no bleeding or spotting, over the 90 days.
Number of bleeding episodes	Number of episodes with one or more consecutive days of reported bleeding, bounded by bleed-free days, within the 90 days
Duration of bleeding episodes	Number of episodes of 2, 3 (etc, to maximum reported) consecutive days with reported bleeding.
Participant-reported side effects	Measured at baseline and day 30, 60 and 90 to assess whether a participant has experienced the side effect and if so the extent of the side effects so that they can be compared to previous timepoints. (Using no/yes "mild", "moderate" or "severe"
Participant reported adherence to trial treatment	Responses will be categorised as all (90/90 pills), most (63-89/90), some (36-62/90), few (1-35/90) and none (0/90). 'Few' and 'None' categories would be classed as treatment non-adherence.
Participant reported discontinuation/removal of their implant	Proportion of participants who report removal of the implant and time to this event.
Participant reported EQ-5D-5L and ICECAP-A	Derived according to published scoring systems.

Participant reported treatment and healthcare usage	Participant Questionnaire
Intention to continue of their allocated treatment after unblinding	Participant Questionnaire

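### Increased blood pressure is collected by participant self-report as present or absent with no follow-up reading scheduled, so never-measured participants can be counted as absent

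*Protocol*

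**What the plan says.** Section 9.2 elicits only selected reactions, on the ground that both products' safety profiles are well known. One of the ten listed is "Increased blood pressure". The list "will be collected on the 30-, 60- and 90-day follow-up questionnaires, completed by the participant", and the section then limits what is recorded: "Only the presence (and severity) or absence of the above will be routinely collected for this trial".

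Table 10 (section 14.2.2) makes participant-reported side effects a secondary outcome, collected "to assess whether a participant has experienced the side effect and if so the extent of the side effects", on a no/yes scale with mild, moderate or severe for yes.

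Table 7 has a row for "Adverse effects of treatment" at days 30, 60 and 90 but no row for blood pressure. The questionnaire contents in sections 8.2.10 and 8.2.11 include no reading. Section 8.2.7 says that "participants will not be required to revisit their sexual health service or GP as part of their participation in this trial". The one planned site contact comes after participation is complete, to reveal the allocation, "either as part of their 3-month standard care visit or via telephone call". No blood pressure reading is specified for it.

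Section 11.3 says that participant-reported data are not queried. Section 14.4.3 presents safety outcomes as counts and percentages.

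**The concern.** Most items on the list, such as headache, nausea or acne, can be noticed and graded by the person who has them. Raised blood pressure generally cannot: both its presence and its severity depend on a reading. A participant whose pressure was not taken during the 90 days has no basis for either answer. If only presence or absence can be recorded, the natural answer is no, which looks the same as a normal reading.

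The trial compares an estrogen-containing pill with a progestogen-only pill, and section 1.1 gives fewer side effects as part of the case for a non-inferiority design. A low percentage over all participants could therefore be read as evidence of little raised blood pressure when it partly reflects little measurement. The loss occurs at data capture. If 'not measured' is never recorded and answers are not queried, no later analysis can recover the denominator.

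**Working it through.** **1. The plan's own figures.** The protocol gives no expected rate for increased blood pressure and no share of participants likely to be measured, so there is no stated figure for this item to reproduce. The sample size does reproduce. With 85% in both arms, a 10-point margin, one-sided 2.5% and 90% power, the Farrington-Manning restricted proportions are 0.7874 and 0.8874, and

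n = [(1.960 × √(0.7874×0.2126 + 0.8874×0.1126) + 1.282 × √(2×0.85×0.15)) / 0.10]² = 275.7, so 276 per arm.

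Then 552 / 0.80 = 690 in total, or 345 per arm. None of this depends on the blood pressure item. The 345 is used below only to turn percentages into counts.

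**2. What can be known at each questionnaire.** Days 30 and 60: no visit is required and no reading is scheduled. Day 90: the same, and the later site contact may be a telephone call. Any reading therefore comes from care outside the protocol's requirements.

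**3. Mechanism.** Let p be the true rate in an arm and m the share with a reading. If unmeasured participants answer no and there are no false positives:

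- reported rate = m × p
- reported difference = m × (p_COCP − p_desogestrel), when m is equal in both arms
- reported risk ratio = p_COCP / p_desogestrel, since m cancels

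**4. Illustration.** The rates of 8% (COCP) and 3% (desogestrel) and the values of m are assumptions.

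| m | COCP | Desogestrel | Difference (points) | Cases per 345 | Risk ratio |
|---|---|---|---|---|---|
| 1.0 | 8.0% | 3.0% | 5.0 | 27.6 vs 10.3 | 2.67 |
| 0.5 | 4.0% | 1.5% | 2.5 | 13.8 vs 5.2 | 2.67 |
| 0.4 | 3.2% | 1.2% | 2.0 | 11.0 vs 4.1 | 2.67 |
| 0.2 | 1.6% | 0.6% | 1.0 | 5.5 vs 2.1 | 2.67 |
| 0.1 | 0.8% | 0.3% | 0.5 | 2.8 vs 1.0 | 2.67 |

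**5. When the risk ratio is not preserved.** If a fraction f of the remaining participants wrongly report it, the reported rate is m×p + (1 − m×p)×f. With f = 1%:

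- m = 0.5: 4.96% vs 2.49%, risk ratio 2.0
- m = 0.2: 2.58% vs 1.59%, risk ratio 1.6

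If m differs by arm, the ratio is multiplied by m_COCP / m_desogestrel. With 0.4 and 0.2 it is 3.2% / 0.6% = 5.3. With 0.2 and 0.4 it is 1.6% / 1.2% = 1.3. Unequal m is possible, because a participant with headaches may be more likely to have her pressure checked.

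**The case against.** **The questionnaire is not shown.** Section 9.2 and Table 10 summarise what is collected; they do not reproduce the response options or say how a blank is coded. A 'don't know' option may exist, and a skipped item might be treated as missing. A reader might infer that every unmeasured participant is scored absent, but the documents do not establish that. What stands is narrower: the text describes presence or absence only, so unmeasured participants can be counted as absent.

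**The size is assumed.** A reader might infer that an arm difference is largely erased. That would require a low m, which the documents do not give, and it concerns the absolute difference only. At m = 0.5 half of the difference remains, and under equal ascertainment without false positives the risk ratio does not move. Nor must the rate be near zero: at m = 0.4 the illustration reports 3.2% and 1.2%.

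**No decision rests on the item.** It is tempting to tie it to the 10% margin. Section 1.1 links fewer side effects to the choice of a non-inferiority design, alongside fewer contraindications, lower cost and other advantages. The margin itself is set in section 14.1 from expert and patient advice about desogestrel's advantages in general. Adverse events are reported descriptively, and serious events are captured separately with site follow-up (section 9.3). In the assumed direction, dilution would understate desogestrel's tolerability advantage, not flatter it.

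**Form design is below protocol level.** This is partly fair. But section 9.2 itself fixes what is recorded, and section 11.3 rules out querying it, so a statistical analysis plan cannot repair the gap afterwards.

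**Conclusion.** The point holds for this one item. As sections 9.2 and 8.2.7 and Tables 7 and 10 stand, a sign that needs a reading is collected by self-report with no reading scheduled, and absence cannot be told from non-measurement. To the extent that unmeasured participants answer no, each arm's percentage and the absolute difference are understated by the unknown factor m. The ratio is protected only under equal ascertainment and no false positives.

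The figures of 8% and 3%, and every value of m, illustrate the mechanism and are not estimates. Nothing is claimed about a baseline reading, because the full list of baseline data is left to the Data Management Plan. The primary outcome, sample size, type I error and margin are unaffected. The change is worth making because it is cheap and the information cannot be recovered once a questionnaire is complete.

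**What to change.** - In the 30-, 60- and 90-day questionnaires, add a 'not measured / don't know' answer to the increased blood pressure item, and amend section 9.2 and Table 10 to match. If the form already has such an answer, only the protocol wording needs aligning.
- Report the item among participants who say that their pressure was measured, with that denominator shown per arm at each time point, alongside the count over all participants.
- Label it in tables as participant-reported awareness of raised blood pressure.
- Report questionnaires completed before the change separately, since their 'no' answers cannot be reclassified.

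The cost is one response option and a table footnote, with no added visit or measurement. The downside is a smaller denominator, self-selected after randomisation, so the comparison among those measured is not protected by the randomisation. That is the reason for keeping the all-participant count beside it.

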### 9.3. Serious Adverse Events and reporting requirements/procedures

The 30, 60 and 90 follow-up questionnaires include questions to ascertain whether a participant has experienced an SAE since they consented to take part in the trial. Where participants have entered information to suggest a reportable SAE e.g. a hospital admission (unplanned), a review of the participants questionnaire will occur, and the recruiting site will be contacted by the NCTU and asked to obtain further information to determine whether an event has occurred that fulfils the SAE criteria. Where a SAE has been experienced, the Principal Investigator (or delegate) must report the SAE on an SAE form to the NCTU. The reporting procedure for an SAE is outlined later in this section.

In instances where a suspected SAE has been reported on the participant questionnaire but the recruiting site has been unsuccessful in contacting the participant to obtain further details, the PI will assess the event based on the information obtained by the research team using medical records and the participant questionnaire. Where the PI deems the event meets the trial SAE criteria, the recruiting site will be required to complete an SAE form and report this to the NCTU within 24 hours of assessment.

AE and potential SAE information will be primarily collected from participants on the 30-, 60- and 90-day questionnaires. Participants may contact the site directly to report a potential SAE that has occurred whilst participating in the trial or may report an SAE during their 3-month standard care review appointment or treatment unblinding phone call. Where a suspected SAE has been reported by a participant, an SAE form must be completed and submitted in line with the trial SAE reporting procedure.

Investigators will report AEs that meet the definition of an SAE. AEs defined as serious, and which require expedited reporting as an SAE, should be reported on an SAE Form. When completing the form, the Investigator will be asked to define the causality and the severity of the AE.

Causality of an event will be categorised as one of the following:

- Definitely related
- Probably related
- Possibly related
- Unlikely to be related
- Unrelated

On becoming aware that a participant has experienced an SAE, the Investigator (or delegate) must complete, date and sign an SAE Form. The form should be emailed to the NCTU as soon as possible and no later than 24 hours after first becoming aware of the event:

To report an SAE, email a copy of the signed SAE form to [[contact]](mailto:[contact]), copying in the DEBI trial inbox [[contact]](mailto:[contact]).

On receipt NCTU will allocate each SAE a unique reference number which will be forwarded to the site as proof of receipt within 1 working day. If confirmation is not received within 1 working day please contact NCTU office. The SAE reference number will be quoted on all correspondence and follow-up reports regarding the SAE and filed with the actual SAE in the Site File and TMF.

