### 8.2.11. 90-day Follow-up Questionnaires

Participants will complete a questionnaire (online, postal or telephone) at 90 days after randomisation which will collect information on the following:

- Bleeding days and episodes
- Perception of their bleeding pattern
- Treatment acceptability
- Global impression of treatment
- Reporting of symptoms and known treatment side effects
- Medications
- Use of health service resources relating to problem bleeding or contraceptive use
- Out of pocket expenses for treatments or products in relation to problem bleeding
- Health Related Quality of life (EQ-5D-5L)
- Capacity-wellbeing (ICECAP-A)
- Intention to continue using implant and allocated trial treatment

At the end of the 90-day participation period, participants will be unblinded to their treatment allocation by their recruiting site. Unblinding will take place at the 3-month standard care visit, or for participants who are unable/unwilling to attend a clinic visit, the recruiting centre will call the participant to reveal their treatment allocation over the telephone. The recruiting centre will be asked to confirm whether the participant intends to continue with their implant and allocated trial treatment (as part of their standard care) once their participation in the trial has concluded.

Completion windows for 30-, 60- and 90-day questionnaires will be 10 days. Questionnaires will no longer be available for completion once outside of the specified completion window; therefore, no protocol deviations will be required for completion of data outside of the specified data collection windows.

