**Table 8-Withdrawal type and procedure post randomisation**

Withdrawal type	Withdrawal procedure	Use of data
Withdrawal from trial treatment	Any participant that requests to discontinue trial treatment will be marked as withdrawn from treatment on the trial database but will be asked to continue to complete questionnaires if willing. Information on reason for stopping trial treatment will be recorded by the site if given, and patient care will continue as part of standard clinical practice.	Any data collected prior to participant withdrawal will be retained and used in the analysis.
Removal of implant	Any participant who notifies the trial or site team that their implant has been removed during their participation in the trial would be withdrawn from the trial and unblinded to their treatment allocation to	Any data collected prior to participant withdrawal will be retained and used in the analysis.

	inform their ongoing contraceptive care. Participants would not be required to complete any further questionnaires or daily diaries but would be followed up for safety outcomes for 7 days following stopping of their trial treatment.	
Withdrawal from daily bleed diary	Any participant that requests to discontinue from daily bleed diary will be marked as withdrawn from diary collection on the trial database and no further MyCap notifications will be sent. Withdrawal from the daily diary does not withdraw from questionnaire completion.	Any data collected prior to participant withdrawal will be retained and used in the analysis.
Withdrawal from follow up questionnaires	Any participant that requests to discontinue from trial questionnaires will be marked as withdrawn from questionnaire collection on the trial database and no further contact relating to questionnaires will be made. Withdrawal from questionnaires does not withdraw from daily diary completion.	Any data collected prior to participant withdrawal will be retained and used in the analysis.
Withdrawal from long-term follow-up	Any participant that withdraws consent for the long term follow-up will be recorded within the database and no long term follow-up data will be collected.	Any data collected prior to participant withdrawal will be retained and used in the analysis.

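### A participant without a day-90 questionnaire gets no unconditional SAE question after the last completed form; the site's closing contact only lets them volunteer one

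*Protocol*

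**What the plan says.** Protocol section 9.3 puts the scheduled SAE questions on the three follow-up questionnaires: "AE and potential SAE information will be primarily collected from participants on the 30-, 60- and 90-day questionnaires". Each form covers the time since consent. The same section adds that a participant may contact the site directly, "or may report an SAE during their 3-month standard care review appointment or treatment unblinding phone call". Once a suspected SAE is reported, an SAE form is mandatory, but nothing there tells the site to enquire.

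The closing contact is described in two places. In 8.2.7, "the site staff will be asked to reveal the treatment allocation to the participant", confirm adherence where possible and confirm whether treatment will continue. In 8.2.11, for those who do not attend, "the recruiting centre will call the participant to reveal their treatment allocation over the telephone", and the site confirms intentions for implant and treatment. Neither list contains an SAE question.

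The day-90 form can be absent for ordinary reasons. Section 8.2.11 gives a 10-day completion window, after which "Questionnaires will no longer be available for completion once outside of the specified completion window". For questionnaire withdrawal, Table 8 states that "no further contact relating to questionnaires will be made", yet "Withdrawal from questionnaires does not withdraw from daily diary completion".

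Two staff-initiated enquiries do not depend on a questionnaire. Section 7.11 provides a welfare check that looks for SAEs when a participant repeatedly reports not taking the pills. Table 8 says that participants whose implant is removed "would be followed up for safety outcomes for 7 days following stopping of their trial treatment".

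**The concern.** All 90 days of medication are dispensed at randomisation and no clinic visit is required before the end (8.2.6, 8.2.7). A participant can therefore stop answering questionnaires, or formally withdraw from them, while still taking the pills and keeping the diary. From the last completed form onward, an SAE in that person reaches the trial only if it is volunteered or if a conditional route happens to apply. The site is nevertheless expected to speak to the same person at the end.

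What is at stake is completeness of safety data. The DMC is to review all SAEs (9.7), all SAEs go annually to the MHRA and REC (9.5.2), and related SAEs are reportable however late they occur (9.4). Those reviews see only what was captured. Safety outcomes are summarised as counts and percentages (14.4.3) among everyone who took at least one dose (14.4.5). A non-responder thus stays in the denominator, and on the stated text an event nobody asked about looks the same as no event. Section 3.3 notes that both drugs are used outside licence and that no trial has evaluated the safety of desogestrel in this use.

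**Working it through.** **Step 1: the plan's own figure.** The inputs from 14.1 are 85% in both arms, margin 0.10, one-sided 0.025, power 0.90 and 20% missing primary outcome. Under the Farrington-Manning score test the restricted null proportions are 0.787 and 0.887. Then s0 = √(0.787×0.213 + 0.887×0.113) = 0.517, s1 = √(2×0.85×0.15) = 0.505, and

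n = [(1.960×0.517 + 1.282×0.505) / 0.10]² ≈ 275.7, so 276 per arm and 552 in total. 552 / 0.80 = 690.

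Both stated figures reproduce. They matter here only for sizing the group.

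**Step 2: planning ceiling.** The primary outcome is collected on the day-90 questionnaire. If a missing item means a missing form (an assumption), 0.20 × 690 = 138 participants could lack it.

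**Step 3: extra time without a scheduled question, relative to a day-90 responder.** Let the day-90 form be completed a days, and the last form b days, into their 10-day windows, with a and b from 0 to 10.

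- Last form day 60: (90 + a) − (60 + b) = 30 + a − b, so 30 days with equal lags, range 20 to 40.
- Last form day 30: (90 + a) − (30 + b) = 60 + a − b, so 60 days with equal lags, range 50 to 70.
- No form completed: no scheduled SAE question at any time.

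Counting instead to the end of the adverse-reaction reporting period in 9.4 (7 days after the day-90 pill, about day 97) gives 97 − 60 = 37, 97 − 30 = 67 and 97 days. That is a different end point, not a conflict.

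**Step 4: every route by which a later SAE could surface.**

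- Telephone completion of the questionnaire (8.2.11): narrows the gap, but ends with the 10-day window or on questionnaire withdrawal.
- Welfare check (7.11): staff-initiated, but only after repeated self-reported non-compliance.
- 7-day safety follow-up (Table 8): staff-initiated, but only after notified implant removal.
- Clinic contact number (8.4.2) and direct contact with the site (9.3): depend on the participant.
- Emergency unblinding (6.4.1): only where knowing the treatment is essential to care.
- Medical-record assessment (9.3): only after a suspected SAE has been entered on a questionnaire and the participant cannot be reached.
- Closing contact (8.2.7, 8.2.11, 9.3): takes place regardless of the questionnaire, but the site is not told to ask.

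None of these is an unconditional enquiry for an adherent participant who simply stops answering forms.

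**The case against.** Nothing in the protocol is contradicted here. Section 9.3 already names the 3-month review and the unblinding call as occasions for reporting, and remote, low-burden follow-up is deliberate (1.1 describes a pragmatic, large simple trial). The questionnaire has three modes. Site staff complete a CRF for the 90-day review (11.2) whose content is not shown and may already hold an SAE item; the monitoring plan behind 7.11 is not shown either. An SAE that made someone stop the pills may surface through the care team (7.7) or the recorded reason for stopping (Table 8). People who ignore a form offered online, by post and by telephone may also be hard for the site to reach.

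Most of this stands as a limit on size. It does not supply a requirement to ask: the further routes are also conditional, and sites may ask in practice without any protocol text obliging them to. Section 9.2 restricts which adverse reactions are elicited; it does not restrict SAE collection.

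Three stronger readings are tempting and are not supported. A reader might infer that no SAE enquiry of any kind follows the last form; 7.11 and Table 8 show otherwise. A reader might take 138 as a forecast of unascertained participants. It is an allowance for a missing outcome item, and it can include complete withdrawals, implant removals and medication withdrawals under Table 12. A reader might also infer that 9.4, 9.5.2 and 9.7 set an ascertainment standard that the trial breaches. They govern SAEs once known.

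**Conclusion.** The point holds in a limited form. Without a completed day-90 form, the protocol requires no unconditional SAE question after the last completed one, and the closing contact, which could fill the gap, is left permissive. The gap is about 30 or 60 extra days depending on the last form, or the whole of follow-up if there was none, for at most 138 of 690 under the planning allowance. The split by last form, the number the site would reach and the number of SAEs missed cannot be derived from the protocol. Events before the last completed form are not lost, because each form asks back to consent.

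This rests on the protocol text alone and on a missing outcome item meaning a missing form. If the 90-day site CRF already carries an SAE item, what remains is to align the protocol wording with it. The primary non-inferiority inference is unaffected. This is a cheap improvement to safety ascertainment, not an error in the analysis.

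**What to change.** In 9.3, replace the permissive clause about the 3-month review and unblinding call with a requirement: at that contact the site asks about any SAE since consent, before revealing the allocation where it is not already known. Add this task to the lists in 8.2.7 and 8.2.11, which at present contain no SAE wording. Record yes, no or not reached on the existing 90-day site CRF if the item is not already there, and check any report against SAEs already received to avoid duplicates.

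At minimum, apply this to participants without a completed day-90 form. Exempt complete withdrawals, because Table 8 rules out further contact. Ask participants with implant removal within their existing 7-day safety follow-up, since they are unblinded at removal. Ask those withdrawn under Table 12 at their end contact, if one takes place.

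The cost is one question at a contact already planned and at most one CRF field, with no extra visit. Site work rises slightly. People who cannot be reached stay unascertained, but they are counted as such.
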